12.10.1 Longitudinal Data

A number of secondary efficacy endpoints will be assessed over time including SOFA total score.

Where appropriate for continuous measures, statistical testing and estimation will be based on the results from a Mixed Model Repeated Measures (MMRM) analysis of covariance (ANCOVA) model. This model will include the baseline value of the outcome variable if appropriate. Other clinically relevant baseline variables predictive of outcome will be considered if there is missing outcome data over time. Inclusion of such covariates helps with the implicit imputation of missing values inherent in the MMRM approach. MMRM is a direct likelihood approach requiring specialized statistical software for optimizing the likelihood function. For this study, all MMRM parameters will be estimated using SAS PROC MIXED version 9.4 or higher [SAS Institute, Cary, NC]. The MMRM model is notable for its ability to include all available data from all eligible subjects and does not require their exclusion as in complete case analysis or arbitrary assignment of values as in LOCF. The MMRM model generally includes a factor for group by time interaction in order to allow group differences in mean values to vary over time. Inclusion of outcome data from all time points informs the implicit imputation of values missing at specific time points through the outcome covariance matrix. Inclusion of baseline covariates has potential for further reduction of potential bias due from missing values.

Specifically, MMRM will be used to compare mean values over time between the 0.50 mg/kg dose and placebo. Model parameters will be estimated using Restricted Maximum Likelihood^{48,49} (REML) as implemented Proc Mixed [SAS Institute, Proc Mixed, SAS/STAT Software]. A generalized Satterthwaite approximation will be used to determine accurate estimates of denominator degrees of freedom for statistical tests. Analyses will characterize changes over time as functions of the baseline value, treatment group, time, and treatment by time interaction. Between-group differences at each time point will be evaluated using contrasts derived from mixed model parameter estimates. This approach produces inferences that are valid under the assumption of missing at random (MAR) which produces valid inference under broader assumptions than complete case analysis or analyses utilizing LOCF⁵⁰.

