12.11.3 SOFA Scores

SOFA scores over time will be assessed as 1) observed cases, 2) LOCF, and 3) using MMRM.

Individually missing SOFA component values due to non-measurement are conventionally assumed as normal and this convention will be followed for this study.

LOCF will not be applied to missing SOFA scores after patient death in analyses that employ LOCF to describe mean values of time. Therefore, analysis of SOFA mean values using LOCF will focus on morbidity rather than mortality.

Mixed model repeated measures analyses will utilize implicit imputed values for all missing values including those subsequent to patient death.

In categorical analyses including formulation of the secondary effectiveness endpoint, total SOFA score at Day 14 ≤ 1 , LOCF is necessary to guarantee that every patient has a value at Day 14.

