10	Deviations from the Original Statistical Plan.....	42
11	Appendix 1: Tables and Listing TOC.....	43
12	Appendix 2: AE Listings.....	52
13	Appendix 3: Patient Listings.....	53
14	Appendix 5: Study Visits and Procedures.....	55
15	Appendix 6: Clinical Score Calculations.....	60
15.1	AKI Staging (KDIGO Criteria).....	60
15.2	Twice the Serum Creatinine for Age, Race, and Gender.....	61
15.3	SOFA – Sequential Organ Failure Assessment Score.....	62
16	Appendix 7: Prior and Concomitant Medications.....	63
16.1	Nephrotoxic Medications.....	63
16.2	Immunosuppressant Medications.....	63
17	Appendix 8: CKD Definition and Classification.....	66
17.1	CKD Definition:.....	66
17.2	CKD Classification.....	66

1 Purpose and Scope of SAP

The purpose of this Statistical Analysis Plan (SAP) is to provide details regarding the analyses sets, endpoints, and statistical analysis methods to be used to meet the objectives of this trial. When differences exist in descriptions or explanations in the Clinical Study Protocol and this SAP, the SAP prevails. This SAP will be finalized prior to unblinding of the treatment allocation codes.

This document is designed to be a stand-alone document in terms of conveying essential statistical approaches to the analysis of the data. Additional definitions and details regarding variables collected are provided in the Clinical Study Protocol.

Statistical approaches were developed to be consistent with accepted statistical and clinical trial principles including ICH E9, Statistical Principles for Clinical Trials¹.

¹ ICH E9 Expert Working Group. Statistical Principles for Clinical Trials: ICH Harmonized Tripartite Guideline. *Statistics in Medicine* 1999; 18:1905–1942.

2 Key Elements of the Analysis Plan

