Mean values and standard deviations (SD) for the SOFA and for the five specific organ components will be summarized over time with and without LOCF. Similarly, mean change scores from baseline (SD) will be summarized with and without LOCF.

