5.11.2 LOCF of Day 28 and Day 90 Creatinine

In order to determine the primary endpoint, freedom from durable loss of eGFR at Day 28, creatinine is necessary. Patients surviving to Day 28 or later but with missing Day 28 creatinine will have their Day 28 creatinine values determined through LOCF. The same procedure will be used for Day 90 Creatinine.

5.11.3 mSOFA Scores

mSOFA scores over time will be assessed as 1) observed cases, and 2) LOCF.

⁶ Cohen, J. (1988). *Statistical power analysis for the behavioral sciences* (2nd ed.). New York, Academic Press.

⁷ Kaplan EL and Meier P. Nonparametric estimation from incomplete observations, *Journal of the American Statistical Association*, **53**:457-481, 1959

⁸ Knickerbocker R. Intent-to-Treat Analyses. In: Chow S-C, ed. *Encyclopedia of Biopharmaceutical Statistics*. Marcel Dekker; 2000.

Individually missing mSOFA component values due to non-measurement are conventionally assumed as normal and this convention will be followed for this study.

LOCF will not be applied to missing mSOFA scores after patient death in analyses that employ LOCF to describe mean values of time. Therefore, analysis of mSOFA mean values using LOCF will focus on morbidity rather than mortality. Also, LOCF will not be used for missing mSOFA after Day 14.

In categorical analyses including formulation of the secondary effectiveness endpoint, total mSOFA score at Day 14 ≤ 1 , LOCF is necessary to guarantee that every patient has a value at Day 14. LOCF will not be performed after patient death.

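### The SAP drops the protocol's baseline-adjusted model for SOFA over time without explanation, leaving this descriptive secondary endpoint with no adjusted between-arm difference

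*SAP*

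**What the plan says.** Protocol 12.10.1 (Longitudinal Data) brings SOFA under its repeated-measures plan: "A number of secondary efficacy endpoints will be assessed over time including SOFA total score". It sets out the model terms: "Analyses will characterize changes over time as functions of the baseline value, treatment group, time, and treatment by time interaction". Between-arm contrasts at each time point are to come from that model. The same section qualifies the baseline term: "This model will include the baseline value of the outcome variable if appropriate". Protocol 12.11.3 then gives the full list of methods: "SOFA scores over time will be assessed as 1) observed cases, 2) LOCF, and 3) using MMRM".

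SAP 5.11.3 (mSOFA Scores) shortens that list: "mSOFA scores over time will be assessed as 1) observed cases, and 2) LOCF". SAP 5.4 describes the output: "Mean values and standard deviations (SD) for the SOFA and for the five specific organ components will be summarized over time with and without LOCF", and "Similarly, mean change scores from baseline (SD) will be summarized with and without LOCF". SAP 8.4 and Appendix 1 carry this into Tables 14.2.4.1 and 14.2.4.2 (scores over time, observed and LOCF) and Tables 14.2.4.3 and 14.2.4.4 (changes from screening, observed and LOCF). No table in the SOFA block of Appendix 1 holds model output.

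SAP section 1 settles which document governs: "When differences exist in descriptions or explanations in the Clinical Study Protocol and this SAP, the SAP prevails". SAP 5.3 names mSOFA over time among the additional secondary endpoints, to be handled in a mainly descriptive way with nominal p-values. The SAP's mSOFA total leaves out the liver component, so it is not the same sum as the protocol's SOFA total.

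**The concern.** The protocol's plan would have given a between-arm difference at each visit, adjusted for where each patient started. The SAP removes that analysis and puts nothing in its place. SAP 5.3 and 5.9 promise nominal p-values and name methods for categorical outcomes, for critical care and hospital stay measures, and for time-to-event outcomes. They name none for mean mSOFA. SAP 5.7 deals with covariates through Mantel-Haenszel or logistic methods, which suit binary outcomes, and screening SOFA is not among the subgroup variables it draws on.

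The screening score is collected before dosing as part of eligibility and can be expected to predict later scores. A raw mean leaves any chance imbalance in that score inside the comparison. A raw change subtracts the whole screening value whatever its true relation to follow-up. At stake is the precision and readability of one descriptive secondary comparison, together with an unexplained difference between the two documents.

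**Working it through.** **The plan's own figures.** The documents give no sizing figure for SOFA. The SAP's only power statement concerns the primary endpoint: 60 per arm, 75% against 50%, one-sided 0.05. With the pooled variance under the null, SE0 = sqrt(2 × 0.625 × 0.375 / 60) = 0.0884 and SE1 = sqrt((0.1875 + 0.25) / 60) = 0.0854. Power is Phi((0.25 − 1.645 × 0.0884) / 0.0854) = 0.890, which matches the stated 89%. This has no bearing on mSOFA.

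**The two documents side by side.**

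- Observed cases: protocol yes, SAP yes.
- LOCF: protocol yes, SAP yes.
- MMRM with baseline, arm, time and arm-by-time: protocol yes, SAP no.
- Use of the screening score: a model term in the protocol; subtraction only in the SAP.

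**Direction of the precision difference.** Take one visit with complete data. Let sB be the SD at screening, sF the SD at follow-up and rho their correlation. Up to a common factor, the large-sample variance of the between-arm difference is:

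- raw follow-up mean: sF²
- change from screening: sF² + sB² − 2·rho·sB·sF
- adjusted for screening: sF²(1 − rho²)

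Raw minus adjusted is rho²·sF², which is never negative. Change minus adjusted is sB² − 2·rho·sB·sF + rho²·sF² = (sB − rho·sF)², which is also never negative. So adjustment is at least as precise as either summary, and this result does not need equal SDs.

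**Size.** The documents give neither rho nor the SDs. Assume sB = sF and rho between 0.3 and 0.7. The ratios to the adjusted variance are 1/(1 − rho²) for raw means and 2(1 − rho)/(1 − rho²) = 2/(1 + rho) for change scores.

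| rho | Raw mean / adjusted | Change / adjusted |
|---|---|---|
| 0.3 | 1/0.91 = 1.10 | 2/1.3 = 1.54 |
| 0.5 | 1/0.75 = 1.33 | 2/1.5 = 1.33 |
| 0.7 | 1/0.51 = 1.96 | 2/1.7 = 1.18 |

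Taking square roots, a confidence interval would be about 5%, 15% or 40% wider from raw means, and about 24%, 15% or 8% wider from change scores, than from the adjusted analysis.

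**The case against.** The strongest defence of the SAP concerns death. Protocol 12.11.3 says that its mixed model implicitly imputes every missing score, including those after death. Protocol 4.1.1 cites 60% mortality for AKI in intensive care. A Day 14 mean from such a model refers to a hypothetical cohort in which nobody dies, and fitting it only to scores recorded before death does not change that. The SAP stops LOCF at death and says its LOCF means concern morbidity. Dropping the model could therefore be a reasoned choice. This stands as a reason not to treat the MMRM as the only remedy. It does not explain why no baseline-adjusted comparison of any kind was kept, and the SAP gives no reason.

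Four further points stand in part:

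- The protocol's commitment was hedged: the model applies where appropriate or possible, and baseline enters if appropriate. Even so, 12.10.1 goes on to list baseline among the model terms.
- The analysis is descriptive, and no test of mSOFA means was sized.
- LOCF is less arbitrary here than usual. Visit 7 in protocol 7.3 asks for SOFA parameters on the day of discharge for patients who leave early, so the carried value should be a discharge-day measurement. Observed cases are shown as well.
- Equal SDs are doubtful. Eligibility requires a total SOFA of at least 2, while follow-up scores can fall to 0 and come only from survivors. This affects the sizes above, not their direction.

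A reader might infer that the SAP discards the screening score. It does not: SAP 5.4 and Tables 14.2.4.3 and 14.2.4.4 report change from screening. A reader might also infer that weaker methods were substituted. Observed-case and LOCF summaries were already in the protocol; the SAP removes the third method.

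**Conclusion.** The point holds as a cheap improvement. The governing document drops a planned baseline-adjusted analysis of a secondary endpoint without explanation, and no adjusted between-arm difference remains. In large samples, adjustment for screening mSOFA is at least as precise as either summary that was kept. By how much cannot be known from the documents: variance ratios of 1.10 to 1.96 for raw means and 1.18 to 1.54 for change scores rest on an assumed correlation of 0.3 to 0.7, equal SDs, a single visit and complete data.

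It would be tempting to restate this as a loss of trial power. The documents do not support that, because no test of mSOFA means is sized, the p-values are nominal, and the primary chi-square test is untouched. The endpoint of total mSOFA at or below 1 on Day 14 is a separate categorical analysis and is also unaffected.

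**What to change.** In SAP 5.4, 5.11.3 and 8.4, add to Tables 14.2.4.3 and 14.2.4.4 a between-arm difference with 95% CI at each visit, from an ANCOVA with screening mSOFA as covariate. Use observed scores in the first table and LOCF up to death in the second. Label the estimate as applying to patients alive at that visit, and report deaths by arm beside it. Keep the existing observed and LOCF summaries. State the visits in one place: SAP 8.4 gives Days 1, 7 and 14 for Table 14.2.4.3, while Appendix 1 adds Day 3.

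If the protocol's MMRM is also restored, label it as implicitly imputing scores after death, not as describing patients while alive. If it is left out, give the reason in a sentence.

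The cost is a short SAP paragraph and one extra estimate per visit in tables already planned, using data already collected. It should be done before unblinding. The small downside is that each estimate is conditional on survival to that visit, which is why the label and the death counts are needed.

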4.2 Secondary Effectiveness Endpoints

The secondary effectiveness endpoints for this study are:

- Freedom from durable loss of renal function at Day 14
- Freedom from durable loss of renal function at Day 90

Reference creatinine values, baseline AKI stage and percentage loss of eGFR at Days 14 and 90 will be determined through algorithmic determination (see details above). Percentage loss of eGFR determined algorithmically will be based on a comparison of eGFR at screening compared to an algorithmically determined reference creatinine value

- Resolution of organ dysfunction (organ resolution is defined as having a total mSOFA score of ≤ 1) at Day 14
- Resolution of specific organ dysfunction (defined as having an individual organ mSOFA score of ≤ 1) at Day 14
- Critical care and hospital stay parameters
 - Hospital length of stay
 - ICU length of stay
 - ICU-free days in 28 days
 - Days on ventilator
 - Ventilator free days in 28 days
 - Vasopressor days
 - Vasopressor free days in 28 days
 - Discharge status

- Patient survival at Days 14, 28 and 90.
- Presentation of Stages 1, 2, or 3 AKI (using the KDIGO criteria)
- **Stratifications involving Day 14 mSOFA \leq 1 vs Day 14 mSOFA \geq 2**
 - Compare critical care between Day 14 mSOFA \leq 1 vs Day 14 mSOFA \geq 2
 - Compare dose groups in those with Day 14 mSOFA \leq 1
 - Compare dose groups in those with Day 14 mSOFA \geq 2
- Among patients presenting with cardiovascular failure (shock), dose group predicting Day 14 mSOFA \leq 1
- Survival to Day 90 as a function of *freedom from durable loss of renal function at 28* (overall and by dose group)

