5.3 Secondary Endpoints

The same analysis as described above will be performed for freedom from durable loss of renal function at Days 14 and 90 and from improvement for freedom from durable loss of renal function as Days 14, 28, and 90.

Additional secondary endpoints include mSOFA over time, critical care and hospital stay parameters (ICU and ICU-free days, ventilator days and –free days, vasopressor days and –free days, and hospital length of stay (LOS)). Analyses for these endpoints will generally be descriptive, with emphasis on characterizing clinical effect sizes. Nominal p-values will be presented. Categorical outcomes will be described using counts and percentages with nominal p-values determined through chi-square or exact methods. Critical care and hospital stay endpoints will be described using non-parametric approaches including using concordance statistics to characterize clinical effect sizes and Wilcoxon rank sum tests to determine nominal statistical significance. Methods appropriate for time-to-event endpoints including survival and life-table methods will be used for time-to-recovery endpoints.

5.4 mSOFA

The Sequential Organ Failure Assessment score or SOFA was originally developed to track a patient's status during a stay in an intensive care unit (ICU)^{4,5}. Each of six organ systems are evaluated and assigned ordinal scores from 0 to 4. A total score is the sum of the component scores. For this study, the liver component is excluded from the sum score and the resulting sum score is referred to in this study as 'mSOFA'.

Several approaches will be taken to summarize changes over time and between treatment groups in the clinical scores as described below. Special handling of mSOFA scores includes the following:

1. If an individual organ score is missing but other scores for that day are non-missing, the organ systems that were not evaluated are assumed to be free of organ failure and given a value of zero when determining the sum score.
2. If all organ scores are missing for a specific day, the mSOFA total score from that day will be imputed using LOCF with the following exception, LOCF will not be performed after patient death.
3. When summarizing the individual organ scores apart from the mSOFA total scores, the same rules as above will apply.

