8.3 Secondary and Exploratory AKI Recovery Endpoints

Table 14.2.2.1 summarizes treatment group comparisons based on secondary AKI recovery endpoints in the mITT analysis set including:

- Freedom from durable loss of renal function at Day 14
- Freedom from durable loss of renal function at Day 90
- Improvement or freedom from durable loss at Day 14
- Improvement or freedom from durable loss at Day 28
- Improvement or freedom from durable loss at Day 90

Tables 14.2.2.2 and 14.2.2.3 repeat these comparisons in the AT and PP analysis sets, respectively.

8.4 mSOFA Scores

Table 14.2.4.1 summarizes observed modified total score, organ specific scores, and mSOFA total scores at Screening, Day 1, Day 3, Day 7, and Day 14.

Table 14.2.4.2 provides the same summary after application of last-value-carried forward (LOCF). LOCF was not applied after patient death.

Table 14.2.4.3 summarizes mSOFA at Screening and changes from Screening to Day 1, Day 7, and Day 14 for observed cases.

Table 14.2.4.4 provides the same summary after application of LOCF.

Table 14.2.4.5 summarizes the percentages of subjects with resolution of organ dysfunction (organ resolution is defined as having a total mSOFA score of ≤ 1) at day 14 and the resolution of specific organ dysfunction defined as having an individual organ SOFA score of ≤ 1 at Day 14.

8.5 Critical Care and Hospital Stay Parameters, to be Measured until Day 28

The following critical care and hospital stay parameters will be assessed.

- Hospital length of stay (days)
- ICU free days
- Days in ICU
- Days on ventilator
- Ventilator free days
- Vasopressors days
- Vasopressors free days
- Discharge status

Because of the expected skewness in the distributions of these parameters, non-parametric Wilcoxon rank sum tests will be used to assess the nominal statistical significance of treatment group differences in these parameters. Table 14.2.5.1 will provide summary statistics by treatment groups including N, mean, median, standard deviation, and minimum, and maximum values.

Table 14.2.5.2 summarizes hospital discharge status.

Table 14.2.5.3 summarizes hospital readmissions.

Table 14.2.5.4 will summarize critical care and hospital stay parameters over days 1 to 28 comparing by primary effectiveness status (success versus failure).

Table 14.2.5.5 will summarize critical care and hospital stay parameters over days 1 to 28 comparing subjects with Day 14 mSOFA ≤ 1 versus Day 14 mSOFA ≥ 2 .

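### SAP 5.11.3 promises every patient a Day 14 mSOFA value but bars carry-forward after death, and no rule says how deaths before Day 14 count in the organ-resolution endpoint

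*SAP*

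**What the plan says.** SAP 4.2 lists the endpoint as secondary: "organ resolution is defined as having a total mSOFA score of" 1 or less at Day 14, with a matching endpoint for each organ. Neither definition mentions survival.

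SAP 5.11.3 sets the missing-data rule for this categorical analysis: "LOCF is necessary to guarantee that every patient has a value at Day 14. LOCF will not be performed after patient death".

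SAP 5.4 covers days on which all organ scores are missing. The total is then imputed by "LOCF with the following exception, LOCF will not be performed after patient death". For single organs it adds: "When summarizing the individual organ scores apart from the mSOFA total scores, the same rules as above will apply".

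On output, SAP 8.4 says: "Table 14.2.4.5 summarizes the percentages of subjects with resolution of organ dysfunction". It gives no denominator. The Appendix 1 table list attaches Tables 14.2.4.5 to 14.2.4.8 to the mITT or PP set, two of them among patients presenting with shock.

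The cut-point is reused to form two groups. Table 14.2.5.5 (SAP 8.5) covers critical care parameters "comparing subjects with Day 14 mSOFA" of 1 or less with those at 2 or more. The same split appears in the stratified analyses of SAP 4.2, the subgroups of SAP 5.6 and 8.8, and the Day 90 life tables in Appendix 1.

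**The concern.** A patient who dies on Day 5, say, has no Day 14 score and may not have one carried forward. That patient is neither resolved nor unresolved, and belongs to neither half of the split at 1 or less versus 2 or more. If the programmer treats the missing value in the usual way, the patient leaves the percentage and the comparison is no longer between the groups as randomised.

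The SAP recognises this problem elsewhere. Section 4.4 explains that a morbidity outcome can look better in the arm with more deaths, and gives no free days for time after death. The primary endpoint requires survival to Day 28. The Day 14 resolution endpoint has neither safeguard.

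The gap arises in the SAP. Protocol 12.11.3 limits the bar on LOCF after death to analyses of mean scores and keeps LOCF for all patients in the categorical endpoint. The SAP adds the bar to the categorical endpoint, and SAP section 1 gives the SAP precedence.

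**Working it through.** **Design inputs.** SAP 2.1.2 plans 60 patients per arm. Its only design figure is 89% power for the primary endpoint (75% versus 50%, one-sided alpha 0.05). This reproduces. The pooled standard error is √(2 × 0.625 × 0.375/60) = 0.0884 and the unpooled one is √((0.75 × 0.25 + 0.50 × 0.50)/60) = 0.0854. Power is Φ[(0.25 − 1.645 × 0.0884)/0.0854] = 0.890. No figure is given for the Day 14 mSOFA endpoint.

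**Assumed inputs.** The documents give no Day 14 mortality or resolution rate for this trial, so all such rates below are assumptions.

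**Formulas.** For an arm with n patients, d deaths by Day 14 and r resolved:
- survivors only: r/(n − d)
- all patients, death counted as not resolved: r/n

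**Equal resolution among all patients.** With 35% resolved in each arm:
- deaths 30% versus 20%: 0.35/0.70 = 50.0% versus 0.35/0.80 = 43.8%
- deaths 25% versus 15%: 0.35/0.75 = 46.7% versus 0.35/0.85 = 41.2%

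The all-patient difference is zero in both cases. With 60 per arm, the first case is 21/42 versus 21/48, uncorrected chi-square p about 0.55.

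**Equal resolution among survivors.** If survivors resolve at a common rate s, the survivors-only difference is zero and the all-patient difference is s × (0.70 − 0.80). At s = 0.45 this is −4.5 points, which the survivors-only table would not show.

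**Whole-patient scenarios, 60 per arm** (arm A is the arm with more deaths):

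| Deaths A / B | Resolved A / B | Survivors only | Difference | All patients | Difference |
|---|---|---|---|---|---|
| 9 / 6 | 24 / 24 | 47.1% vs 44.4% | +2.6 | 40.0% vs 40.0% | 0 |
| 12 / 6 | 24 / 24 | 50.0% vs 44.4% | +5.6 | 40.0% vs 40.0% | 0 |
| 24 / 12 | 24 / 24 | 66.7% vs 50.0% | +16.7 | 40.0% vs 40.0% | 0 |
| 18 / 6 | 22 / 24 | 52.4% vs 44.4% | +7.9 | 36.7% vs 40.0% | −3.3 |
| 18 / 6 | 19 / 24 | 45.2% vs 44.4% | +0.8 | 31.7% vs 40.0% | −8.3 |

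The last row has close to equal resolution among survivors (about 45%). The lowest survivors-only p-value in the table is 0.127 (24 versus 12 deaths).

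**The case against.** A reader might infer that the endpoint, as written, compares survivors only. The documents do not go that far. No section states the denominator, and Table 14.2.4.5 is assigned to the mITT set. If all mITT patients are counted, a patient without a qualifying score is simply not a responder, which is the result wanted. The stated aim that every patient has a value also points away from deliberate exclusion. SAP 8.4 does say "LOCF was not applied after patient death", but that sentence describes Table 14.2.4.2, the LOCF summary of scores over time, and is not evidence about the yes/no table. This objection stands: exclusion is one reading, not a stated rule. It does not remove the contradiction, and it leaves the result to a programming choice. Where the SAP intends a table of survivors, as in Tables 14.2.5.7 and 14.2.5.8, it labels it so. The resolution tables have no such label to warn the reader.

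A reader might also infer that the rule manufactures a benefit for the arm with more deaths. That depends on the assumed pattern. With equal resolution among survivors there is no false benefit, only concealed harm. Nor do the documents suggest more deaths on active treatment. In the Phase 2 study (Protocol 4.1.3.3.2) 2 of 32 dosed patients died on Reltecimod and 2 of 11 on placebo, in a different population and over 28 days. If that direction held, dropping deaths could work against Reltecimod.

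Finally, the endpoint is one of many secondaries that SAP 5.3 calls generally descriptive, with nominal p-values. Survival at Days 14, 28 and 90 is reported, with mortality life tables by arm. This also stands and limits the consequence.

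**Conclusion.** The contradiction in SAP 5.11.3 is certain from the text, as is the absence of any rule for deaths before Day 14 in SAP 4.2, 5.4, 5.11.3 and 8.4. That deaths would leave the comparison is conditional on an unstated denominator.

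If they did leave, the whole-patient scenarios with equal numbers resolved give a spurious difference of 2.6 to 16.7 points in favour of the arm with more deaths. The true direction can also be reversed (+7.9 reported against −3.3), or a deficit of 8.3 points can be all but hidden. These sizes rest on assumed death and resolution counts and show what is possible, not what is expected.

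The primary endpoint is unaffected. The point should be corrected before unblinding, but it does not threaten the trial's main conclusion.

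**What to change.** - In SAP 5.4 and 5.11.3, state that death on or before Day 14 counts as not resolved, for the total mSOFA and for each organ.
- For Tables 14.2.4.5 to 14.2.4.8, state that the denominator is every patient in the named analysis set, or in its shock subset where that applies. A survivors-only result may be added as supportive if it is labelled so and shown with deaths by arm.
- State how early deaths are classed wherever the Day 14 split at 1 or less versus 2 or more is used: Table 14.2.5.5, the stratified analyses in SAP 4.2, the subgroups in SAP 5.6 and 8.8, and the Day 90 life tables. The answer need not be the same everywhere. In the life tables, placing early deaths in the group at 2 or more would raise that group's mortality by construction, so a start at Day 14 among those alive may be preferred.
- Do not simply return to the rule in Protocol 12.11.3. Under it, a patient who died after a last score of 1 or less would count as resolved.

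The cost is a few sentences in the SAP and matching table footnotes. No new data are needed, because survival is already recorded at each visit through Day 14.
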